#### 11. SAFETY

#### 11.1. Safety Parameters

#### 11.2. Adverse Event Definition

#### 11.2.1 Adverse Events

An AE is any untoward medical occurrence in a patient or clinical investigation subject administered a medicinal product and which does not necessarily have to have a causal relationship with this treatment. An AE can therefore be any unfavorable and unintended sign (including an abnormal laboratory finding), symptom, or disease temporally associated with the use of an IP, whether or not related to the IP.

Worsening of a pre-treatment event, after initiation of tazemetostat, must be recorded as a new AE. For example, if a subject experiences mild intermittent dyspepsia prior to dosing tazemetostat, but the dyspepsia becomes severe and more frequent after the first dose of tazemetostat, a new AE of severe worsening dyspepsia (with the appropriate date of onset) should be recorded in the eCRF.

"Lack of efficacy" or "failure of an expected pharmacological action" *per se* is not to be reported as an AE or SAE. However, any signs and symptoms and/or clinical sequelae resulting from "lack of efficacy" will be reported as an AE or SAE, if they fulfill the definition of an AE or SAE.

Events that **do not** meet the definition of an AE include:

- Medical or surgical procedure (e.g., endoscopy, appendectomy); the condition that leads to the procedure is an AE.
- Situations where an untoward medical occurrence did not occur (social and/or convenience admission to a hospital).
- Anticipated day-to-day fluctuations of pre-existing disease(s) or condition(s) present or detected at the start of the study that do not worsen.

## 11.2.2 Serious Adverse Events

An SAE is any untoward medical occurrence that, at any dose:

- a. Results in death
- b. Is life-threatening

**NOTE:** The term 'life-threatening' in the definition of 'serious' refers to an event in which the subject was at risk of death at the time of the event. It does not refer to an event, which hypothetically might have caused death, if it were more severe.

c. Requires hospitalization or prolongation of existing hospitalization

**NOTE:** In general, hospitalization signifies that the subject has been detained (usually involving at least an overnight stay) at the hospital or emergency ward for observation and/or treatment that would not have been appropriate in the physician's office or out-patient setting. Complications that occur during hospitalization are AEs. If a complication prolongs hospitalization or fulfills any other serious criteria, the event is serious. When in doubt as to whether "hospitalization" occurred or was necessary, the AE should be considered serious.

Hospitalization for elective treatment of a pre-existing condition that did not worsen from baseline is not considered an AE.

d. Results in disability/incapacity, or

**NOTE:** The term disability means a substantial disruption of a person's ability to conduct normal life functions. This definition is not intended to include experiences of relatively minor medical significance such as uncomplicated headache, nausea, vomiting, diarrhea, influenza, and accidental trauma (e.g., sprained ankle) which may interfere or prevent everyday life functions but do not constitute a substantial disruption.

e. Is a congenital anomaly/birth defect.

Medical or scientific judgment should be exercised in deciding whether reporting is appropriate in other situations, such as important medical events that may not be immediately life threatening or result in death or hospitalization but may jeopardize the subject or may require medical or surgical intervention to prevent one of the other outcomes listed in the above definition. These should also be considered serious. Examples of such events are intensive treatment in an emergency room or at home for allergic bronchospasm, blood dyscrasias or convulsions (in subjects without pre-existing seizure disorder) that do not result in hospitalization, or development of drug dependency or drug abuse.

#### 11.3. Laboratory Abnormalities

A clinical laboratory AE is any laboratory value that is considered clinically significant by the investigator and has caused a medical intervention or is accompanied by clinical symptoms. Laboratory abnormalities that have not required medical intervention should not be recorded as AEs and will be captured and reported in the laboratory section of the clinical study report (CSR). If a medical intervention occurs, it should be recorded as a treatment with the abnormal

laboratory finding as the AE (e.g., anemia with treatment required and blood transfusion recorded as a procedure, hyperglycemia with treatment required and change in insulin dose recorded on concomitant medications).

The investigator should decide, based upon the AE criteria and the clinical condition of the patient, whether a change in a laboratory parameter is clinically significant and therefore represents an AE.

If, at the end of the treatment phase with the study drug, there are pathological laboratory values which were not present at baseline, further clinical or laboratory investigations should be performed until the values return to within reference range or until a plausible explanation (i.e., concomitant disease) is found for the pathological laboratory values.

### 11.4. Other Safety Assessment Abnormalities

Other safety assessments (e.g., ECGs, radiological scans, vital signs measurements), including those that worsen from baseline and events in the medical and scientific judgment of the investigator are considered to be clinically significant, are to be recorded as an AE or SAE, in accordance with the definitions provided in Sections 11.2.1 and 11.2.2, respectively.

Any other safety assessment that led to an intervention, including permanent discontinuation of study treatment, dose reduction, and/or dose interruption/delay is also to be recorded as an AE or SAE.

#### 11.4.1 Disease-Related Events

Events that meet the criteria for serious but are thought to be associated with progression of the disease under study should be reported as SAEs but will not typically be processed as expedited reports to regulatory authorities.

**NOTE:** Disease progression *per se* should not be reported as an SAE.

#### 11.5. Adverse Events of Special Interest (AESIs)

For this study, AESIs will include:

- Occurrence of T-cell lymphoma (refer to Section 11.10 for instructions on continued reporting of these events). Refer to Section 4.3 for management of secondary lymphoma
- Events considered related to abnormal bone formation and confirmed by radiologic scan.

• AEs associated with treatment overdose, misuse, abuse, or medication error; and any treatment-emergent significant laboratory abnormality.

These AESIs are to be captured using the SAE procedures but are to be considered as SAEs only if they met one of the above criteria.

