- q. **Post-Treatment/Early Termination:** A Post-Treatment/Early Termination visit will be conducted within 30 days (±3 days) after the last dose of tazemetostat or prior to the start of a new treatment or therapy at the end of study or if the subject's participation is terminated early. The post-treatment/early termination assessments will be required and, in the event of a continuing AE, the subject will be asked to return for follow-up until the AE has resolved or is deemed to be continuing indefinitely.
- r. **Follow-Up:** Survival follow-up will be conducted approximately every 12 weeks on all subjects, unless they withdraw consent. Information on all anticancer therapies will be collected (the sponsor may choose to stop the collection of therapies after the first anti-cancer treatment following tazemetostat). This may be done by telephone contact.

Table 2: Timing Allowance Windows for Vital Sign Measurements, Pharmacokinetic Sampling, and ECG Measurements

Vital Signs	
Timepoint	Tolerance Window
0 hour	-60 min to 0 hour

Pharmacokinetic Sampling	
Timepoint	Tolerance Window
0 hour	-120 min to 0 hour
>0 hour – 3 hour	-5 minutes/+5 minutes
4 hour – 8 hour	-15 minutes/+15 minutes
10 hour – 12 hour	-30 min/+30 min
24 hour	-60 minutes/+60 minutes

ECG	
Timepoint	Tolerance Window
0 hour	-60 min to 0 hour
>0 hour – 1 hour	-10 minutes/+10 minutes

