# 4.3. Rules for Suspension of Enrollment

The investigators, IRBs/ECs, regulatory agencies and IDMC will be urgently informed and the IDMC convened to review the data and to make recommendations for potential changes in study conduct if one or more subjects develop any of the following AEs deemed to be definitely related to study treatment by the investigator and/or medical monitor, based upon close temporal relationship or other factors:

- Death
- Anaphylaxis (angioedema, hypotension, shock, bronchospasm, hypoxia or respiratory distress)
- Secondary lymphoma

Should study enrollment be suspended, the study will not be restarted until all parties have agreed to the course of action to be taken and the IRBs/ECs have been notified.

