#### 7.3. **Dose Modification**

No modification of dose is required for the following  $\geq$  Grade 3 non-hematologic toxicities:

- Transient fatigue or asthenia lasting < 24 hours
- Transient myalgia or arthralgia lasting < 24 hours
- Nausea that resolves to < Grade 2 within seven days (with or without anti-emetics)
- Vomiting that resolves to < Grade 2 within 48 hours (with or without anti-emetics)
- Diarrhea that resolves to < Grade 2 within 48 hours

Other toxicities that, in the opinion of the investigator, are possible, probably or definitely related to study treatment, should be managed per Table 3. Toxicities that are felt by the investigator to be unrelated to tazemetostat but clinically significant should be discussed with the medical monitor. In the event of an urgent unrelated toxicity, study treatment should be interrupted as per Table 3. Dose re-escalation is not permitted.

Of note, in the event of an occurrence of a secondary neoplasm, including T-cell lymphoma, study treatment will be permanently discontinued. See Sections 4.3 and 11.5 or further discussion.

occur only after discussion with medical monitor

Dose Adjustmentb Toxicitya **During Therapy** Grade 1 Continue study treatment Maintain dose level All occurrences Grade 2 All occurrences Continue study treatment Maintain dose level **Grade 3c (Not Including Neutropenia)** 1st occurrence Restart at 600 mg BID Interrupt study treatment until 2nd occurrence resolved to Grade ≤1 or baselineb Restart at 400 mg BID (same or new toxicity) 3rd occurrence Discontinue study treatment Not applicable (same or new toxicity) Grade 3 Neutropenia (ANC:  $<1-0.5 \times 10^9/L$ ) Maintain dose level 1st occurrence Interrupt study treatment until Restart at 600 mg BID 2nd occurrence resolved to ANC  $\geq 1.0 \times 10^9/L$ 3rd occurrence Restart at 400 mg BID Discontinue study treatment 4th occurrence Not applicable Grade 4d Resumption of dosing may

**Table 3:** Dose Modifications for Treatment-Related Toxicities

ANC = absolute neutrophil count; BID = twice daily

All occurrences

Hold study treatment

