# 11.9. Timeframe for Reporting AEs and SAEs

**AEs:** AEs will be collected from the time the first dose of study treatment is administered until the earlier of either 30 days after the discontinuation of study treatment or until the initiation of subsequent anti-cancer therapy.

**SAEs:** SAEs will be collected over the same time period as stated above for AEs. In addition, any SAE assessed **as related** to study participation (e.g., protocol-mandated procedures, invasive

tests, or change in existing therapy), study treatment must be recorded from the time a subject provides consent to participate in the study up to and including any follow-up contact. All SAEs will be reported to the sponsor within 24 hours.

After discontinuation of study treatment: The investigator will monitor all ongoing AEs/SAEs until resolution or stabilization of the event or until the subject is lost to follow-up or has withdrawn consent. Up until 30 days after the last dose of study treatment or until the initiation of subsequent anti-cancer therapy, whichever is earlier, the Investigator will report any AE that they consider to be possibly related to study treatment.

Note that any incidence of secondary lymphoma, even if occurring more than 30 days after the last dose of study drug, will be reported to the Sponsor as an SAE.

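### Four sections define the secondary-cancer risk in three different ways, and two give conflicting SAE rules; other secondary cancers are left out of the AESI outputs, and some late ones are not collected

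*Combined protocol and SAP*

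**What the plan says.** The protocol deals with secondary cancers in four places.

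- **Section 7.3, Dose Modification:** "in the event of an occurrence of a secondary neoplasm, including T-cell lymphoma, study treatment will be permanently discontinued". It then directs the reader onward: "See Sections 4.3 and 11.5 or further discussion".
- **Section 4.3, Rules for Suspension of Enrollment:** the committee is convened "if one or more subjects develop any of the following AEs deemed to be definitely related to study treatment". The only cancer on the list that follows is secondary lymphoma.
- **Section 11.5, AESIs:** the only malignancy listed is "Occurrence of T-cell lymphoma (refer to Section 11.10 for instructions on continued reporting of these events". AESIs go through the SAE procedures but "are to be considered as SAEs only if they met one of the above criteria".
- **Section 11.9, Timeframe for Reporting:** "any incidence of secondary lymphoma, even if occurring more than 30 days after the last dose of study drug, will be reported", and it is to go to the sponsor as an SAE.

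Section 11.9 also sets the general window. AEs and SAEs of every kind are collected from first dose until 30 days after stopping treatment, or until new anti-cancer therapy if that comes first. Beyond that window, an SAE is still recorded at any follow-up contact if it is assessed as related.

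Section 13.5.2 summarises and lists treatment-emergent events of special interest. It has no separate output for secondary malignancies.

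**The concern.** Section 2.3.4 treats secondary lymphoma and other secondary cancers together when it says that neither had been seen in treated subjects. Section 7.3 uses a similarly broad term. The sections that decide what is flagged, what is followed late and what is tabulated use narrower terms that also differ from one another. A site that follows the reference in 7.3 arrives at two sections that do not cover the term used in 7.3.

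Two things are at stake. First, someone looking for secondary cancers in the AESI outputs could see none although one had occurred. Second, some late cases would never reach the database, and no later analysis could recover them. Separately, a site that diagnoses a T-cell lymphoma finds two rules for classifying it and a reference to a section that does not contain the instruction it promises.

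**Working it through.** The plan states no figure on this point, so the check sets the passages side by side.

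**Step 1: event scope by section**

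| Event | 7.3 (treatment ends) | 4.3 (committee convened) | 11.5 (AESI) | 11.9 (late reporting) |
|---|---|---|---|---|
| T-cell lymphoma | yes | only if definitely related | yes | yes, always an SAE |
| Other secondary lymphoma | yes | only if definitely related | no | yes, always an SAE |
| Other secondary cancer | yes | not named | no | only if serious and judged related |

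These are three scopes: any secondary neoplasm (7.3), secondary lymphoma (4.3 and 11.9) and T-cell lymphoma (11.5). The condition in 4.3 is also awkward to apply, because Section 11.7.1 records relationship only as related or not related, and definite relationship is merged into the first category.

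**Step 2: the SAE rules.** Take a T-cell lymphoma that meets no criterion in Section 11.2.2. Under 11.5 it is not an SAE. Under 11.9 it is, since that rule applies "even if occurring more than 30 days after the last dose of study drug, will be reported to the Sponsor as an SAE", and the opening words show that earlier cases are covered too. Section 11.2.2 does not list secondary cancer as a criterion. Such a case would be serious through death, hospitalization or another listed outcome, or by judgment as an important medical event.

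**Step 3: the cross-reference.** Section 11.10 gives general SAE and SUSAR reporting duties and contains no instruction on continued reporting of T-cell lymphoma. That instruction is the closing note of 11.9, which is worded for secondary lymphoma.

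**Step 4: what is still counted.**

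- A secondary cancer inside the window is an AE and, under 13.5.2, is tabulated by system organ class and preferred term.
- If it arises on treatment, 7.3 ends treatment, so it also enters the summary and listing of events that led to discontinuation.
- If it is serious, it enters the serious-event outputs.
- After the window, any secondary lymphoma is reported, and so is any other secondary cancer that is serious and judged related.

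**Step 5: what is left.**

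- (a) A non-T-cell lymphoma or other secondary cancer is not a listed AESI, so it is absent from the AESI summary and listing even when it was collected.
- (b) A non-lymphoma secondary cancer that arises after the window closes, and is judged unrelated or non-serious, is not required to be collected.

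**Step 6: would follow-up reveal (b)?** The follow-up row in Table 1 is for disease assessment and survival. Footnote r adds anti-cancer therapies, but "the sponsor may choose to stop the collection of therapies after the first anti-cancer treatment following tazemetostat". Section 10.2 covers survival, and Section 10.4 covers response to later therapy where possible. None of these names a new malignancy as something to ask about.

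**The case against.** The strongest reply is that different purposes may need different definitions. Stopping a drug, convening a committee, flagging an event for special attention and extending follow-up need not share one term. The AESI follows the preclinical signal, which was lymphoma in rats, and Section 2.3.4 mentions other secondary cancers only as not observed. That is a fair defence of having more than one scope. It does not explain why 7.3 refers to sections that omit its own term, or why the AESI is limited to T-cell lymphoma when Section 2.3.1 does not describe the rat lymphoma as T-cell.

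A second reply is that the SAE conflict has little practical effect. AESIs already follow the SAE procedures, 11.9 is the more specific rule, and a new lymphoma would probably be judged serious. This largely stands: no lymphoma is lost. The classification still depends on which section a site reads.

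A third reply is that the contact form may ask about new cancers, and that Section 13.3.3 leaves full analysis detail to the SAP. The form is not among the documents, so this cannot be excluded. The SAP can add a table, but it cannot tabulate what the protocol does not require sites to collect.

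A reader might also infer that lymphoma is the only cancer reported late, or that the trial cannot inform the statement that no secondary cancers have been seen. The documents support neither. The related-SAE rule in 11.9 covers any cancer, and a zero in the AESI row can sit beside a secondary cancer shown elsewhere in the 13.5.2 outputs.

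**Conclusion.** The point holds as an inconsistency with a narrow consequence for data capture. Three scopes, two SAE rules for T-cell lymphoma and one wrong cross-reference can be verified from the text. The consequences are that the AESI outputs omit every secondary cancer except T-cell lymphoma, and that a late non-lymphoma cancer judged unrelated or non-serious is not collected. Because the trial is single-arm, there is no comparison group against which to check the attribution of a late cancer, and attribution is one of the judgments on which collection depends.

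The size cannot be given as a number, because the documents state no human rate of secondary cancer and no expected number of late, unrelated cases. A reader might take the rat lymphoma counts, or a confidence bound for zero cases among the maximum of 67 subjects, as a measure. Neither measures this gap. The rat finding concerns lymphoma, which 11.9 already follows without time limit, and a bound for zero cases assumes that all cases were found.

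The conclusion assumes that sites apply the protocol as written and that the follow-up form has no item on new malignancy. If such an item exists, gap (b) shrinks but the wording still needs aligning. No view is taken on which event should end treatment or suspend enrollment.

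**What to change.** 1. In 11.5 and 11.9, use one event term for data capture. Secondary neoplasm, already the term in 7.3, would serve, with T-cell lymphoma as a subcategory.
2. In 11.9, apply the reporting beyond 30 days to that term, whatever the attribution and whether or not new anti-cancer therapy has begun.
3. State one SAE rule for these events and use it in both sections.
4. Correct the reference in 11.5 from 11.10 to 11.9.
5. Add one yes/no item on any new malignancy since the last contact to the existing 12-weekly follow-up contact.
6. In 13.5.2, tabulate secondary malignancies separately, with cases after the treatment-emergent window shown apart. Section 13.5.2 gives that window a start but no end, so the end should be stated.
7. The sponsor should reconcile 4.3 with 7.3, including the reference from one to the other and the relationship category that 4.3 relies on.

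The cost is protocol wording, one case report form item and one table, with no new visit. The drawback is that a few background cancers, such as skin cancers, will be reported as AESIs.

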#### 11.6. Grading and Severity

The severity of all AEs and SAEs, including appropriate laboratory values, will be graded utilizing the CTCAE v4.03. The link to the CTCAE Version 4.03 is:

http://evs.nci.nih.gov/ftp1/CTCAE/CTCAE\_4.03\_2010-06-14\_QuickReference\_8.5x11.pdf

In the event that an AE is not covered by the CTCAE, the assessment of severity will be determined by using the CTCAE general guideline:

Grade 1:	Mild; asymptomatic or mild symptoms; clinical or diagnostic observations only; intervention not indicated.	
Grade 2:	Moderate; minimal, local or noninvasive intervention indicated; limiting age-appropriate instrumental ADL. a	
Grade 3:	Severe or medically significant but not immediately life-threatening; hospitalization or prolongation of hospitalization indicated; disabling; limiting self-care ADL. b	
Grade 4:	ade 4: Life-threatening consequences; urgent intervention indicated.	
Grade 5:	Death related to AE	

ADL = Activities of Daily Living; AE = adverse event

Instrumental ADL refer to preparing meals, shopping for groceries or clothes, using the telephone, managing money, etc. Self-care ADL refer to bathing, dressing and undressing, feeding self, using the toilet, taking medications, and not bedridden.

An AE that is assessed as severe should not be confused with an SAE. Severity is a category used for rating the intensity of an event (as in 'mild', 'moderate', or 'severe'); both AEs and SAEs can be assessed as severe. An event is described as 'serious' when it meets one of the predefined outcomes as described in Section 11.2.2 which are based on patient/event outcome or action criteria associated with events that pose a threat to a subject's life or functioning

#### 11.7. Relationship Categorization

A qualified investigator must make the determination of relationship to tazemetostat for each AE or SAE. The investigator should decide whether, in his or her medical judgment there is a reasonable possibility that the event may have been caused by tazemetostat.

